### Secondary outcomes

All secondary outcomes are based on the mITT population unless otherwise specified. The following secondary outcomes will be explored:

- The difference in differences (DID) in HAM-D6 score, from baseline to end of study, between participants in:
  1. TAU-GP and ALGO
  2. TAU-GP-and TAU-P
  3. TAU-P and ALGO
- The DID in C-SSRS score, from baseline to end of study, between participants in:
  1. TAU-GP and ALGO
  2. TAU-GP-and TAU-P
  3. TAU-P and ALGO
- The DID in MDI score, from baseline to end of study, between participants in:
  1. TAU-GP and ALGO
  2. TAU-GP-and TAU-P
  3. TAU-P and ALGO
- The DID in PSP score, from baseline to end of study, between participants in:
  1. TAU-GP and ALGO
  2. TAU-GP-and TAU-P
  3. TAU-P and ALGO
- The impact of the assigned treatment pathway from the participant's point of view and the participant's personal experience of recovery through a self-rating scale (Brief INSPIRE-O). This will also be done using the DID, from baseline to end of study, between participants in:
  1. TAU-GP and ALGO

2. TAU-GP-and TAU-P

3. TAU-P and ALGO

- The concordance between MDI and HAM-D6.
- Duration of sick leave after baseline (indicated in days) within the current depressive episode.
- A Per Protocol analysis at week 12 (PP12) will also be completed for all continuous secondary outcomes.
- A Per Protocol analysis at week 12 (PP12) will also be completed for the primary outcome.
- Between-group difference for adverse events and serious adverse events.
- Between-group difference for the ITT population in reasons for premature discontinuation, time to all-cause discontinuation

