## Patient Population

### Study population

Participants will include patients from general practice diagnosed with unipolar depressive disorder by a general practitioner, in which there is clinical uncertainty as to which of the initial treatments (medication or psychotherapy) would be most beneficial. Patients will be aged 18 to 65 at baseline.

Participants will be recruited from multiple general practices in the North Denmark Region by their general practitioner. 171 participants will be included with an expected dropout rate of 20%.

Symptomatic remission (i.e. remitters) is evaluated using the Hamilton Rating Scale for Depression, 6 item version (HAM-D6) and is defined as a score  $\leq 5$  (20). Symptomatic response (i.e. responders) is also evaluated using the HAM-D6 and is defined as a 50% reduction in the HAM-D6 score. For further details, see figure 2.

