## Statistics and Power Calculation

### Statistics

The difference in HAM-D6 score between baseline and follow up will be compared between the three groups. A F-test will be used to assess if there is a significant difference among the groups. The analysis will be applied to the mITT population using last-observation-carried-forward (LOCF).

The three different treatment groups will be directly compared to each other, i.e. TAU-GP against ALGO, TAU-GP against TAU-P and TAU-P against ALGO. The groups will be compared based on the change in HAM-D6 scores from baseline to endpoint using a two-sided t-test (difference-in-differences [DID] analysis), along with other relevant secondary outcomes.

The DID-analysis will be applied to the mITT population at 12 weeks using LOCF, and the PP12 population.

In secondary analysis, differences between treatment groups regarding changes during the study period for each of the HAM-D6, MDI, PSP, C-SSRS, and Brief INSPIRE-O scores, will be analysed in separate mixed effects models. The models will be analysed with the relevant outcome as dependent variable, and time, treatment, and their interaction as fixed effects as well as patient and centre as random effects, also using the mITT and PP12 populations.

The proportion of responders (defined as a 50% reduction of HAM-D6 score) or remitters (defined as a HAM-D6 score  $\leq 5$ ) will be compared between the three groups, using chi-square tests for association and/or Poisson regression with a robust estimation of the standard error. The same will be applied to the remaining categorical variables. The analyses will be performed by using the mITT population. A similar analysis will be carried out for the categorical variable reasons for treatment discontinuation in the ITT population.

Further, risk of adverse events and serious adverse events is compared by applying Poisson regression with a robust estimation of the standard error in the mITT population.

To investigate the differences in time to all-cause discontinuation and duration of sick leave after baseline between the three groups, compared two and two, the time in the study will be compared by applying a two-sided t-test. Analysis of sick leave days is carried out on the mITT population and time to all-cause discontinuation will be performed on the ITT population.

Concordance between HAM-D6 and MDI will be analysed visually.

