Exploratory analyses will extend the primary linear mixed-effects model by adding baseline variables (age, sex, educational level, baseline HAM-D6, duration of untreated depression, age at first episode, psychiatric/physical comorbidity, prior treatment history and DART score). If deemed feasible, non-linear dynamics as the interaction with treatment arm or an estimation using splines will be included. Relevant effects will be reported as regression coefficients or odds ratios with 95 % CIs and visualised in stratified plots where relevant.

All model assumptions are checked visually and sensitivity analyses, using bootstrap to estimate standard errors, are conducted in case of any violations.

All secondary outcomes will be analysed regardless of the significance of the primary outcome.

The statistical analyses will be performed by a statistician at the Department of Psychiatric Research, Aalborg University Hospital, Psychiatry, using Stata 19.

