#### Power calculation

To detect a clinically relevant difference of at least 2.25 points of HAM-D6, with a power of 0.80 and a significance level of 0.05 (two-sided), 45 patients are required in each of the three groups (27, 28). To further account for an estimated dropout of 20%, a total of 57 patients are needed in each group.

The standard deviation of the difference in HAM-D6 between baseline and 12 weeks of treatment is assumed to be equal to 3.9 in all three groups (29).

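### Concordance between MDI and HAM-D6 is a secondary outcome, but the only stated method is visual, so the protocol commits to no estimate or confidence interval for it

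*Protocol*

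**What the plan says.** The Secondary outcomes section introduces its list with "The following secondary outcomes will be explored", and one item is "The concordance between MDI and HAM-D6". The Statistics section gives the method in a single sentence: "Concordance between HAM-D6 and MDI will be analysed visually". It also commits the trial to analysing every item on the list: "All secondary outcomes will be analysed regardless of the significance of the primary outcome".

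The Table of Measurements schedules both HAM-D6 and MDI at baseline and at weeks 4, 8 and 12. Table 1 describes HAM-D6 as an interview rating and MDI as a self-report questionnaire.

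**The concern.** Had the protocol been silent on method, the choice could be presumed to lie with the statistical analysis plan. It is not silent. It names a method, and that method by itself commits to no numerical result. No type of plot, visit, measure or standard of concordance is given, so what is reported would rest largely on the reader's impression of a graph after the data are seen.

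What is at stake is modest. A listed secondary outcome could reach publication without an estimate or a statement of its uncertainty, although the data for one are already being collected.

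**Working it through.** **Step 1. Does another planned analysis supply the estimate?** The numerical analyses in the Statistics section that involve either scale are these:

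- The F-test and pairwise t-tests compare change between arms, one scale at a time.
- The mixed models take HAM-D6, MDI and the other scales in separate models, with time, treatment and their interaction as fixed effects. None relates one scale to the other.
- Responder and remitter comparisons use HAM-D6 only.
- The one sentence that promises intervals, "Relevant effects will be reported as regression coefficients or odds ratios with 95 % CIs", belongs to the exploratory models with baseline variables.

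None of these measures how HAM-D6 and MDI relate within patients. The visual analysis is the only one stated for this outcome.

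**Step 2. How many pairs would there be?** The protocol states no figure for concordance, so there is none to reproduce. Its sample size supplies the inputs.

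- The Power calculation section gives 45 per group before dropout. Inflating for 20% dropout: 45 / (1 − 0.20) = 56.25, rounded up to 57, as the protocol states.
- All randomised: 3 × 57 = 171, as stated under Study population.
- After dropout: 3 × 45 = 135.

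The range is therefore about 135 to 171 patients overall, or 45 to 57 per arm, with one pair of ratings per patient at a given visit.

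**Step 3. What precision would a numerical measure have?** A Pearson correlation is used for illustration. The protocol gives no value of r, so r is an assumption and a range is shown. The Fisher z interval is

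tanh( atanh(r) ± 1.96 / √(n − 3) ).

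Worked case, r = 0.7 and n = 135: atanh(0.7) = 0.867; 1.96 / √132 = 0.171; the limits on the z scale are 0.697 and 1.038, which transform back to 0.60 and 0.78.

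| Assumed r | 95% CI, n = 135 | 95% CI, n = 171 |
|---|---|---|
| 0.5 | 0.36 to 0.62 | 0.38 to 0.61 |
| 0.7 | 0.60 to 0.78 | 0.61 to 0.77 |
| 0.9 | 0.86 to 0.93 | 0.87 to 0.93 |

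Within one arm, r = 0.7 gives about 0.51 to 0.82 with n = 45 and about 0.54 to 0.81 with n = 57. Results by arm are therefore descriptive.

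Sample size is no reason to omit an estimate.

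**Step 4. What would such an estimate not show?** If ratings in one arm were shifted by a constant c, then corr(HAM-D6 + c, MDI) = corr(HAM-D6, MDI), so the correlation within that arm would not move. The measure describes how the scales track each other. It does not test for rating bias.

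**The case against.** The strongest reply is that the sentence on visual analysis does not exclude a statistic beside the plot, and that plot type, visit and accompanying numbers are details an analysis plan commonly adds. This stands in part. It cannot be said that the trial will have no estimate, only that the protocol commits to none. It does not remove the point, because the protocol fixes a method rather than leaving it open.

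A second reply is that the outcomes are to be explored, with no threshold or decision attached to concordance, so a graph is a weak choice rather than an invalid one. That is fair, and it is why the point is minor.

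A reader might infer two stronger things, and the documents support neither:

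- **That a plot can yield no figure at all.** Some agreement plots carry a mean difference and limits of agreement. The protocol names no plot type, so this cannot be ruled out.
- **That, in this open-label trial, distortion of the rated outcome could not be checked without a concordance estimate.** The protocol already plans MDI comparisons for all three pairs of arms, and mixed models for MDI alongside HAM-D6. Setting the arm effects on the two scales side by side is the more direct check. A correlation within an arm would miss a constant shift. MDI is also completed by participants who know their treatment, so close agreement would not exclude a bias common to both scales.

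**Conclusion.** The point holds as a minor one. Concordance between MDI and HAM-D6 is a listed secondary outcome, its only stated method is visual, and the protocol as written commits to no estimate or confidence interval for it. The primary analysis, sample size and treatment comparisons are unaffected.

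The precision figures rest on assumed correlations, one pair per patient and the planned numbers. They show that a useful estimate is available. They do not predict what it will be.

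**What to change.** Keep the plots and prespecify one numerical measure with a 95% CI, calculated on observed pairs rather than carried-forward values. Name one visit, for example week 12, and add change from baseline to that visit. Report it overall, and by arm as description only.

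- The two instruments differ, so either use a correlation and call it association, or use an agreement measure on standardised scores.
- If visits are pooled, allow for repeated ratings on the same patient.
- Add kappa for response only if an MDI response definition is first stated. The protocol defines response on HAM-D6 alone.
- Keep it short. All four visits plus three changes from baseline, in three arms and overall, would be (4 + 3) × (3 + 1) = 28 coefficients, more than this outcome warrants.

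The cost is a sentence or two of wording before analysis and a little extra analysis. No new data are needed.

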#### Power calculation

To detect a clinically relevant difference of at least 2.25 points of HAM-D6, with a power of 0.80 and a significance level of 0.05 (two-sided), 45 patients are required in each of the three groups (27, 28). To further account for an estimated dropout of 20%, a total of 57 patients are needed in each group.

The standard deviation of the difference in HAM-D6 between baseline and 12 weeks of treatment is assumed to be equal to 3.9 in all three groups (29).

#### Handling and Storage of Data

All trial data will be registered in the electronic Case Report Form (eCRF) and source data on paper (e.g. notes, diagnostic interviews, etc.) will be stored in a room at the site, secured under a two-lock system.

The eCRF will be divided to differentiate material from baseline, week 4, week 8, and week 12, as well as material from the qualitative study.

Source data will be preserved for a minimum of 5 years after completion of the study, and all electronic data are preserved for 15 years, after which the data will be given to the Danish Data Archive.

All data will be registered online in a database, REDCap, centrally administered by North Denmark Region, with central personal registry numbers. Registration will happen on the site and data will be entered directly into REDCap. The database (REDCap) is approved by the Data Protection Agency and is used in other research projects.

Study participants will be given an identification number relating to the eCRF. The identification number will follow the participant throughout the period of the trial. The numbers are used for export of anonymous data and all identifiable data are treated confidentially. Further, the identification list is registered in the site file.

The information in the database and in the eCRF are kept together with personal registry numbers.

## Data Protection

The study complies with the General Data Protection Regulation (GDPR) and is a part of North Denmark Region's record of processing activities (under §30).

Both the sponsor and the principal investigator will be responsible for the upholding of data protection regulations regarding the processing of personal data within the study.

The study will also be registered in the *Psychiatry of North Denmark Region's List of Research Projects*, according to internal rules.

## Risk and Side Effects

All treatments used in the study, medications and cognitive behavioural therapy (CBT), are approved treatment options in Denmark and have been used in the treatment of depression. Regarding medication, trial participants will primarily receive treatment with antidepressants. All medication is administered by the individual patient's general practitioner.

Common side effects of antidepressants include nausea, headaches, sleep disturbances i.e. insomnia or excessive sleepiness, weight changes and sexual dysfunction (30).

Information about the different medication will be provided by the general practitioner in question, as well as follow up regarding the medication and potential side effects.

## Biological Material

In this research project, no biological material will be required. If a general practitioner finds that there is indication for, e.g., blood samples, it will be at the discretion of the respective GP to administer, interpret, store, and act upon such initiatives.

The results of blood tests will be accessible for the study staff through the participant's medical record.

## Information from Patient Medical Record

All study participants are recruited from general practice, and their medical records are stored in the respective clinics' systems. These medical records are not directly accessible to the study staff or investigator, however, during the participant's treatment course, the investigator will be granted permission to access the patient's current list of medications through Fælles Medicinkort (FMK).

Further, a medical record for each of the participants will be created in the official medical record system, Elektronisk Patient Journal (EPJ), related to Aalborg University Hospital. The records will occur under the Department of Psychiatric Research.

Through EPJ, it will be possible to communicate with general practitioners through correspondence letters regarding a specific patient and to obtain relevant information about the participant and their treatment course. Throughout the trial period, the study staff will be granted access to information about participants.

After the participants sign the written letter of consent, all information concerning their treatment and medical history will be used in the study, including previous diagnoses and medications, as well as adverse events, hospital, and outpatient visits. This is necessary to create the most accurate and safe treatment plan for the patient, which is central to the study's purpose.

The declaration of consent will grant the sponsor-principal investigator and the sponsor's representatives, including relevant regulatory authorities, direct access to retrieve relevant information from the participants' medical records and electronic health records.

This access is granted to allow review of relevant information on the study participant's health status, as it is necessary for the execution of the project and for oversight purposes.

This includes internal audits, quality control, and monitoring.

## Funding and Financing Budget

The study is initiated by [name] [name]., PhD., professor and Chief Physician from Aalborg University Hospital, Department of Psychiatry.

Funding is partially achieved through the *Independent Research Fund Denmark* (DFF). The remaining part will be financed through external funds, with a deficit guarantee from the Department of Psychiatry South, Aalborg University Hospital.

The estimated total budget for this project is 4.1 million DKK.

Budget overview				
The budget figures are collected from the uploaded spreadsheet file				
	DFF-financing	Co-financing	Other sources	Total (DKK)
Applicant		648.420		648.420
Scientific/academic staff excluding postdocs and PhD students		59.880		59.880
Postdoc(s)				
PhD-student(s)	1.700.634	600.000		2.300.634
Total scientific/academic	1.700.634	1.308.300		3.008.934
Technical/administrative staff	219.361	374.863		594.224
Equipment expenses				
Operating expenses	279.876	236.000	27.360	543.236
Total - excl. overhead	2.199.871	1.919.163	27.360	4.146.394
Overheads	68.196	n/a	n/a	68.196
Total (DKK)	2.268.067	1.919.163	27.360	4.214.590

Table 2: Illustrates the total budget amount.

Amount for scientific/academic salaries:	1.700.634 kr.
Amount for technical/administrative salaries:	219.361 kr.
Amount for equipment:	0 kr.
Amount for operating expenses:	279.876 kr.
Amount applied for excl. overhead/administration expenses:	2.199.871 kr.
Amount for overhead/administration expenses:	68.196 kr.
Amount applied for incl. overhead/administration expenses:	2.268.067 kr.

Table 3: Illustrates the funding from the Independent Research Fund Denmark (DFF).

## Publication of Results

All findings, whether positive, negative, or inconclusive, will be published.

Publication will take place in scientific journals, on [www.clinicaltrials.gov](http://www.clinicaltrials.gov), or [www.clinicaltrialsregister.eu](http://www.clinicaltrialsregister.eu), and the results will also be presented at an international scientific conference.

Currently, three publications are planned concerning this study:

1. A publication of the study protocol
2. A publication on the primary outcome of the study
3. A publication on the secondary outcomes of the study

The authors of the primary publications are expected to be [name] as first author and [name] as last author. Other co-authorships will be assigned and offered in accordance with the ICMJE criteria.

## Scientific Ethics and Significance

### Ethics

Participation and treatment in the study do not involve greater risk for the participants than that associated with the average clinical practice, and all medications used for treatment in the study are approved pharmaceuticals by the Danish health authorities and are commonly used in the treatment of depression.

All three of the study models (TAU-GP, TAU-P, and ALGO) are acknowledged as efficient treatment choices for depression and supported scientifically in the literature as well as in clinical practice.

The participants will help improve the current knowledge about treatment for depression in general practice and potentially help to elucidate which treatment path is most beneficial for future patients with depressive episodes.

If the participants have accepted to receive a letter with the results of the study, such will be sent to them after the completion of the entire study.

### Potential significance

The insights gained from this study could significantly enhance the understanding of specific patient traits and their relation to treatment for depression, but also potentially alter the approach currently used in general practice regarding treatment of depression.

Successfully identifying individual characteristics in relation to depression holds great promise in the field of depression treatment. Specific patient traits could perhaps guide future treatment decisions. By understanding the unique psychological profile of individuals with depression, clinicians can optimise medication selection, dosage, and treatment modalities. This approach may enhance treatment outcomes by minimising side effects and reducing the trial-and-error process associated with finding the right treatment.

It could ultimately lead to improved treatment for depression in general practice and enhanced patient outcomes.

The results of the study could potentially impact which form of treatment should be used in the future, when treating patients with moderate depression in general practice, and hopefully lead to optimised treatment and possibly reducing direct as well as indirect healthcare costs.

### Patient Insurance and Compensation

All participants in the study are covered consistent with the law on patient insurance and the law on patient compensation.

Participants will not receive any renumeration or reimbursement for taking part in the trial.

